4.2.2 Completion of the Woman on-line questionnaires by the woman

There will be one online questionnaires to be completed by women, which will be different from that for HCPs.

A single questionnaire will be completed by the woman, where data on pregnancy diagnosis, exposure to ella®, and if known at the time of the questionnaire completion, the pregnancy outcome. If not known at the time of the first completion, the woman will have the option to get back to the questionnaire and continue its completion when the outcome will be known.

For live birth, woman will also be requested to complete a follow-up questionnaire 4 months after the delivery date (**4-month Follow-Up Woman Form**).

The language of the woman questionnaire will be further adapted to facilitate understanding and format will have functional ergonomics that are permitted by online data entry such as linked questions, drop-down menus, and agenda for fill in dates. In addition, some of the questions will integrate a specific tutorial for helping the declarant to enter appropriate answers. Contents of the information requested in the woman questionnaires are detailed in a specific distinct document submitted to the IRB for its approval prior to implementation.

Women who do not want to provide their HCP contact details, will have the option to contact a referent physician who will be commissioned to follow-up directly with the women. Referent physician will be able to answer their questions and guide them through the questionnaire completion process. The referent physician will not be able to complete the woman questionnaire on their behalf.

4.2.3 Enrolment enhancement

In addition to changing the way the study is conducted, the following actions will be carried out to enhance the enrolment of ella®-exposed pregnant women in the USA:

- A dedicated website will provide a complete description of the study for Ella®-exposed women and HCP as well as access to reporting forms.
- HCP and ella®-exposed pregnant women will primarily be made aware of this study through information in the Product Labelling [Prescribing Information (PI) / Patient Leaflet (PL)]. Introduction of the website address in PI and PIL will help HCP and women to have direct access to the on-line study.
- Promotional information for HCP will include a reminder on the existence of the pregnancy study.
- Links to the study website will be made from the product and company websites.
- A reminder to HCP about the existence of the study could also be done at the following occasions:
 - Information to HCP by sales representatives;
 - Local, national and international scientific meetings/conferences/congresses;
 - Continuing education sessions for medical professionals;
 - Contacting relevant professional organizations;
 - Registering the study on pregnancy registry website (such as the FDA Office of Women's Health (OWH) pregnancy registry website).

4.3 Inclusion criteria

Women meeting all the following criteria will be considered for admission to the study:

- Pregnant women in the USA, exposed to ella® during the menstrual cycle in which the pregnancy started (treatment failure) or at any time during pregnancy (inadvertent exposure during pregnancy)
- Written informed consent provided:
 - When the questionnaire is completed by the HCP, the ICF will be downloaded from the website and 2 print-out copies signed by the woman. One signed copy will be given to the woman for her records.
 - When completed by the woman, an electronic signature will be requested on the ICF module and the woman will be requested to save and/or print-out the ICF for her records.

5 INFORMATION ON ella® SUPPLY

HRA Pharma will not supply any medication. Women will be enrolled after having taken commercially available ella®.

6 MEDICAL HISTORY

Maternal medical history related to previous pregnancies or any other relevant medical history will be reported by the HCP or woman questionnaire.

Family history of hereditary or other birth defect will also be collected.

7 PRIOR AND CONCOMITANT MEDICATIONS

Any relevant medication (prescription or non-prescription), including hormonal contraceptive, taken from the Last Menstrual Period (LMP) and up to pregnancy outcome will be collected in the HCP or woman questionnaire.

HRA Pharma's Pharmacovigilance department may contact the reporter to collect additional relevant information needed for the appropriate evaluation of a case.

8 STUDY PROCEDURES AND SCHEDULE

8.1 Overview of safety data

Pregnancy information

Date of diagnosis, date of LMP, date and results of ultrasound (if applicable) and expected delivery date.

Exposure to ella®

Data on exposure to ella® include date of ella® intake and number of tablets taken, time from intercourse to ella® intake; pregnancy stage at ella® exposure, pregnancy status before ella® intake.

Outcomes

All outcomes and the data collected to assess them are:

- Live birth – gender, birth weight, gestational age, delivery method and Apgar scores will be collected in all cases. For healthy babies and those with congenital anomalies or other neonatal diagnosis, the study observation period will last until 4 months after delivery;
 - Congenital anomaly or other neonatal diagnosis – description of anomaly and possible causes will be additionally collected;
 - Neonatal death (from birth through to 28 completed days of age*) – age at death, possible etiology and result of autopsy if performed will be additionally collected.
- Pregnancy loss – gestational age, possible etiology of pregnancy loss and any complications (vaginal bleeding, need for curettage, infection) will be collected in all cases.
 - Spontaneous abortion (or early fetal death i.e. < 20 completed weeks of gestation*)
 - Ectopic pregnancy
 - Induced abortion (no medical reason – woman's elective choice, elective abortion with fetal defects, or maternal health complications)
 - Stillbirth:
 - Intermediate fetal death (more than 20 completed weeks of gestation but less than 28*)
 - Late fetal death (\geq 28 completed weeks of gestation*).

Maternal health complications of pregnancy

In all cases, relationship of the outcome observed with the exposure to ella® will be assessed by the HCP and according to the standard pharmacovigilance process.

* According to the WHO International Classification of Disease (ICD)

Prior and concomitant medications

Prior and concomitant medications will be collected in the HCP or women questionnaires. Collection period covers the pregnancy duration from LMP to the end of pregnancy.

Other

Maternal family history; recreational drug use (tobacco, alcohol, illicit drugs) and serological and prenatal tests.

8.2 Description of study steps

Depending upon the questionnaire (HCP or woman), the following information will be collected through the questionnaires' completion either directly from the woman or by the HCP.

8.2.1 Completion of the on-line questionnaire by the HCP

Depending upon the outcome, there will be different forms to be completed on-line by the HCP and for live birth only, 4-month Follow-Up HCP Forms will have to be completed as well.

8.2.1.1 Website access and registration

At the first website access, the HCP will be requested to:

- Register on the website, a user identifier and a password (to be changed at the first login) will be sent by e-mail to the HCP. HCP will be requested to use this login to access the on-line questionnaire;
- Complete the on-line training;
- Fulfil administrative steps: download and acknowledge Confidentiality Agreement reading, as well as the Study protocol.

8.2.1.2 Enrolment Steps

Prior to enroll a woman, the HCP will have to:

- Download the Information Sheet from the website, to be given to the woman during the consultation;
- Download the ICF and the HIPAA Authorization agreement from the website and print it out;
- Enroll the woman by collecting her signature on the ICF and HIPAA agreement and give her a copy of the signed documents.

After enrolment, the HCP will access the on-line questionnaire and will be asked to:

- Collect the woman contact details to ensure future follow-up of the pregnancy outcome (first 3 characters of the last name and first character of the first name,), date of birth, weight and height. If applicable, the contact details of the clinician/midwife in charge of pregnancy follow-up should also be collected (see also section 8.3 Participant follow-up)
- Collect information on pregnancy [including date of diagnosis, date of LMP, date and results of ultrasound (if applicable), expected delivery date]
- Collect data on ella® exposure (date of ella® intake, number of tablets taken, time from unprotected intercourse to ella® intake, pregnancy stage at exposure and pregnancy status before ella® intake)

- Collect relevant current or prior medication during the pregnancy, including hormonal contraception or folic acid at the time of conception
- Collect any relevant medical condition (including maternal health complications) observed preceding or during pregnancy
- Save and submit the questionnaire

8.2.1.3 Completion of the Pregnancy Outcome Forms

When the outcome of the pregnancy is known*, the HCP will be asked to fill-in the Pregnancy Outcome forms.

- Access the website with the HCP unique user ID and password
- Start the Pregnancy Outcome Form completion
- Collect the pregnancy outcome observed [live birth (i.e. healthy baby, congenital anomaly, neonatal death) including pregnancy complications, pregnancy loss (including spontaneous abortion, ectopic pregnancy, therapeutic abortion, intermediate or late fetal death), maternal health complications]
- Collect recreational drug use (tobacco, alcohol, illicit drugs), if any
- Collect relevant maternal and family medical history, including history related to previous pregnancies, including congenital birth defects
- Collect serology and prenatal tests (type, date, results)
- Collect relevant concomitant medications
- Save and submit the forms.

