All cases will be managed according to the sponsor's Pharmacovigilance processes, in line with the applicable legislation.

Whenever applicable, individual case safety reports (ICSRs) will be submitted to Health Authorities on an expedited basis according to current regulations.

Progress status updates will be given in each Periodic Safety Update Report (PSUR) and Development Safety Update Report (DSUR) if applicable.

Additionally, a descriptive analysis of the data collected will be provided annually in the PSUR.

Study duration and dates

Recruitment of women will be done using a website access. Implementation of the website is planned for the second quarter of 2014 and website will be in place during the whole course of the study.

STUDY SCHEDULE

Period of pregnancy Study procedures	Enrolment in the study	Pregnancy Course	End of pregnancy	4 months FU ³
Written ¹ informed consent	X			
Inclusion criteria	X			
Pregnancy diagnosis	X			
ella [®] exposure	X			
Prior and concomitant medications	X	X	X	
Recreational drug use (tobacco, alcohol, illicit drugs)	X	X	X	
Serology and prenatal tests results	X			
Medical history	X			
Maternal and fetal pregnancy complication	X	X	X	
Pregnancy outcome ²			X	
Live birth follow-up ³				X

¹: Signed ICF will be collected according to local regulations. When completed by the HCP, prior starting the questionnaire completion, the ICF will be downloaded from the website and a print-out copy signed by the woman. When completed by the woman, prior starting the questionnaire completion, an electronic signature will be requested on the ICF module and the woman will be requested to save and/or print the ICF for her records.

²: Possible pregnancy outcomes are: Live birth (healthy baby, congenital anomaly or other neonatal diagnosis, or neonatal death); pregnancy loss (spontaneous abortion or ectopic pregnancy or induced abortion, premature stillbirth)

³: In case of live birth, the period of observation of the study will last for 4 months post-delivery to access possible congenital anomalies that may not be detected at birth.

ABBREVIATIONS AND DEFINITIONS

ADR	Adverse Drug Reaction
AE	Adverse Event
AFP	Alpha-Fetoprotein
CFR	Code of Federal Regulations
CHMP	Committee for Medicinal Products for Human Use
CRO	Contract Research Organization
DMB	Data Monitoring Board
DSUR	Development Safety Update Report
EC	Emergency Contraception
EUROCAT	European Surveillance of Congenital Anomalies

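### The study schedule and the HCP forms disagree on when drug use, family and obstetric history, and prenatal tests are collected, and the HCP text records the first two only once the outcome is known

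*Protocol*

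**What the plan says.** The Study Schedule at the end of the synopsis has these rows:

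- "Recreational drug use (tobacco, alcohol, illicit drugs": marked at enrolment, pregnancy course and end of pregnancy.
- "Serology and prenatal tests results": marked at enrolment only.
- "Medical history": marked at enrolment only.

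Section 8.2.1.2 sets out what the HCP enters after enrolment: identifying details with date of birth, weight and height; pregnancy dating; ella exposure; medication, including folic acid at conception; and medical conditions ("Collect any relevant medical condition (including maternal health complications) observed preceding or during pregnancy"). It names no drug use, family or obstetric history, serology or prenatal tests.

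Section 8.2.1.3 applies when the outcome is known; at that point "the HCP will be asked to fill-in the Pregnancy Outcome forms". Its list contains:

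- An item on history: "Collect relevant maternal and family medical history, including history related to previous pregnancies, including congenital birth defects".
- An item on substance use: "Collect recreational drug use (tobacco, alcohol, illicit drugs), if any".
- An item on tests, which opens: "Collect serology and prenatal tests (type, date, results".

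Sections 4.2.1 and 8.4 describe the same two-step order for HCPs: diagnosis and exposure first, the remainder once the outcome is known.

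**The concern.** A site or a database builder cannot follow both the schedule and section 8.2.1. If the HCP text is followed, drug use and family/obstetric history are asked about by someone who already knows whether there was a loss, an anomaly or a healthy baby. Those answers depend on what is asked and what is recalled or admitted, so knowledge of the outcome can change them.

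The items matter in two places. Section 9.2.2.4 plans multi-variable models of risk factors for adverse outcomes, partly to judge whether events can be put down to known risk factors and to suggest groups needing precautions. Section 11.1 has the Data Monitoring Board (DMB) take associated risk factors into account when it decides whether a complication could be linked to ella. If reporting depends on outcome, a factor could be given too much or too little of the blame.

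The timing also affects completeness. A woman enrolled by an HCP and then lost to follow-up never reaches the outcome form, so these items would be missing for her. An analysis plan cannot recover information that was not captured before the outcome.

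**Working it through.** **Step 1. Item-by-item comparison for the HCP route**

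| Item | Study Schedule | HCP enrolment (8.2.1.2) | HCP outcome form (8.2.1.3) | Result |
|---|---|---|---|---|
| Recreational drug use | Enrolment, course, end | Not listed | Listed | Conflict at enrolment and course |
| Serology/prenatal tests | Enrolment | Not listed | Listed, with dates | Conflict; no shared time point |
| Medical history | Enrolment | Medical conditions listed; family and obstetric history not listed | Maternal, family and obstetric history listed | Partial conflict |
| Medications | Enrolment, course, end | Listed | Listed | Agree at both ends |

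The medications row shows that the protocol can place an item on both forms when that is intended.

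**Step 2. Does any other step carry out the schedule's marks?** Section 8.3 has the HCP contacted at 20 weeks and at the scheduled delivery date and asked to complete the questionnaire. Section 14.1 describes the 20-week contact as seeking information on outcome. Under section 4.2.1 the remaining items wait for the outcome. No described HCP step collects drug use during the pregnancy.

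**Step 3. Who is affected?** Section 8.4 allows completion from diagnosis up to a known outcome.

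- HCP-reported, enrolled before outcome: drug use and family/obstetric history are deferred until the outcome is known. This is the affected group.
- First reported when the outcome is already known: the answers follow the outcome under either version.
- Woman-reported: section 8.2.2.2 places drug use in her own questionnaire, which section 4.2.2 lets her start before the outcome and return to later.
- Pooled spontaneous reports (section 9.2.1): not governed by these forms.

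**Step 4. How large could the distortion be?** The protocol gives no prevalence or reporting sensitivity, so the following rests on assumptions. Take a factor with true prevalence 20% and no effect, no false-positive reports, and sensitivity between 70% and 90%. The reported prevalence is 0.20 × sensitivity, that is 14%, 16% or 18% for sensitivities of 70%, 80% or 90%. The apparent odds ratio is the odds of a report after an adverse outcome divided by the odds after a normal one.

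| Sensitivity after adverse / normal outcome | Calculation | Apparent odds ratio |
|---|---|---|
| 90% / 70% | (0.18/0.82)/(0.14/0.86) | 1.35 |
| 90% / 80% | (0.18/0.82)/(0.16/0.84) | 1.15 |
| 90% / 90% | (0.18/0.82)/(0.18/0.82) | 1.00 |
| 80% / 90% | (0.16/0.84)/(0.18/0.82) | 0.87 |
| 70% / 90% | (0.14/0.86)/(0.18/0.82) | 0.74 |

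Both directions are shown because reporting after an adverse outcome could be fuller (closer questioning) or poorer (reluctance to admit use). The table shows how the distortion would behave. It does not estimate its size in this study.

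**The case against.** The strongest reply is that this is a small inconsistency whose consequences are easily exaggerated. The primary analysis in section 9.2.2.2 is a set of unadjusted proportions with exact intervals, which uses none of these items. Section 9.2.2.4 names no covariates and makes the models conditional on a sufficiently large sample, and section 11.1 does not list its risk factors. The odds ratios above only restate whatever gap in sensitivity is assumed. All of that stands, and it keeps the point minor.

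A reader might also infer more than the protocol supports:

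- *That women lost to follow-up have no risk-factor data, so completers cannot be compared with them.* Section 8.2.1.2 collects date of birth, weight, height, medication, folic acid and medical conditions at enrolment, and section 9.2.2.1 describes baseline characteristics of both enrolled and completed cases. For HCP-enrolled losses, what is missing is drug use, family/obstetric history and tests.
- *That HCPs are asked for all history only after the outcome.* Medical conditions are asked for at enrolment; only family and obstetric history is deferred.
- *That prenatal tests are open to recall bias.* They are dated records. Section 8.2.1.3 would capture later tests that the schedule's enrolment-only mark would omit, so the fault there is the contradiction.
- *That the models should use enrolment values alone.* This would discard later drug use, which the schedule intends to capture.

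None of these limits removes the contradiction, or the fact that the HCP text gives up outcome-blind recording of drug use and family/obstetric history where prospective enrolment would allow it.

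**Conclusion.** The point holds as a minor one. The schedule and sections 8.2.1.2 and 8.2.1.3 contradict each other on recreational drug use and on serology/prenatal tests, and partly on medical history. That rests on the text alone and needs no assumption.

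The bias is a reasonable inference, confined to drug use and family/obstetric history in HCP-reported pregnancies enrolled before outcome. It assumes that the forms are built as section 8.2.1 describes, that knowledge of the outcome alters reporting, and that these factors are among those used in the models or weighed by the DMB. Its size cannot be derived from the protocol: the illustrative odds ratios for a null factor run from 0.74 to 1.35, with 1.00 if reporting does not depend on outcome. The unadjusted outcome proportions are not affected.

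**What to change.** 1. Reconcile the Study Schedule with sections 8.2.1.2 and 8.2.1.3, so that each item has the same collection points in all three.
2. Add recreational drug use and maternal, family and obstetric history to the HCP enrolment form, and keep them on the outcome form as an update.
3. Mark serology and prenatal tests in the schedule at every point where they are collected, including end of pregnancy.
4. Record, for each risk factor, whether it was reported before or after the outcome was known. Use that flag in the models or in a sensitivity analysis, and retain the updates made after enrolment.

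The cost is moving or duplicating a few items between two online forms, adding a timing flag and correcting one table; the HCP enrolment form becomes slightly longer. The gain is limited to HCP-reported pregnancies enrolled before outcome. Pregnancies first reported at a known outcome and pooled spontaneous reports are not helped, although the flag would at least identify the former within this study.

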8.2.1.4 Completion of the 4-month Follow-Up HCP Forms

In case of live birth and 4 months after the delivery, the HCP be reminded to re-access the website. The HCP will be asked to:

- Access the website with the HCP unique user ID and password
- Collect the age, height and weight of the baby
- Collect congenital anomaly detected since birth, if applicable
- Collect late development detected since birth, if applicable
- Collect death data, if applicable.

8.2.2 Completion of the on-line questionnaire directly by the woman:

Up to three questionnaires will be completed by the woman: the first two ones including Pregnancy and Outcome Forms, and one for live birth only, a 4-month Follow-up Form.

* In case a woman completed the questionnaire on her own, she should be reminded to bring her unique patient number to allow the HCP to provide further information on the pregnancy if requested.

8.2.2.1 Website access and enrolment

- Access the website
- Download the Information Sheet from the website, read it and acknowledge its reading and understanding
- Download the ICF from the website, acknowledge its reading and understanding by signing it electronically
- Read inclusion criteria and get enrolled by saving or printing-out the signed ICF, to be kept for the woman's records
- By signing and saving and/or printing out the ICF, the woman will be considered as enrolled in the study.

8.2.2.2 Completion of the Pregnancy and Outcome Forms

- Access the on-line questionnaire
- Provide first 3 characters of her last name and first character of her first name, date of birth, e-mail address (which will be blinded to the sponsor), her weight and height
- Provide information on pregnancy [including date of diagnosis, date of LMP, date and results of ultrasound (if applicable), expected delivery date]
- Provide data on ella® exposure (date of ella® intake, number of tablets taken, time from unprotected intercourse to ella® intake, pregnancy stage at exposure, additional ella® intake)
- Provide relevant concomitant medications taken during the pregnancy, including hormonal contraception or folic acid at the time of conception
- Report any relevant medical condition preceding or during pregnancy (e.g. diabetes, hypertension)
- Provide the pregnancy outcome observed [live birth (including healthy baby, congenital anomaly, neonatal death), pregnancy loss (including spontaneous abortion, ectopic pregnancy, therapeutic abortion, intermediate or late fetal death)]
- Provide recreational drug use (tobacco, alcohol, illicit drugs), if any
- Provide HCP details*. If the woman is not willing to provide her HCP details, she will be invited to contact a referent physician for assistance in the completion of the questionnaire
- Save and submit the questionnaire
- A unique patient number will be sent by e-mail to the woman, to be used for further access to the website. The woman will be able to further access her file at any time by using her unique patient number and continue the questionnaire completion when additional follow-up data is known.

